1.1. Synopsis

Protocol Title: A Multicenter, Long-term, Open-label Study to Evaluate the Safety of MT10109L (NivobotulinumtoxinA) for the Treatment of Glabellar Lines and Lateral Canthal Lines

Protocol Number: MT10109L-004

Brief Title: MT10109L in the Long-term Treatment of Glabellar Lines and Lateral Canthal

Lines

Study Phase: 3 Study Rationale:

The purpose of this open-label, extension study is to evaluate the long-term safety of repeated MT10109L treatment of GL and/or LCL in participants with moderate to severe GL, LCL, or both (GL and LCL) who completed the lead-in pivotal Phase 3 studies (MT10109L-001, -002, -005, and -006) over an additional 24 months.

Objectives and Endpoints:

Objective	Endpoints		
Primary			
To evaluate the long-term safety of repeat treatments of MT10109L in participants with moderate to severe GL, LCL, or both (GL and LCL)	 Incidence of adverse events, change from baseline in vital sign parameters, and presence of binding and neutralizing antibodies 		

Overall Study Design:

•	This is a multicenter, open-label, repeat treatment study to evaluate the long-term s MT10109L in treating GL, LCL, or both (GL and LCL).	safety of
_		

 All participants who complete studies MT10109L-001 (GL), MT10109L-002 (LCL), MT10109L-005 (GL with or without LCL), and MT10109L-006 (LCL with or without Gwill be eligible to enroll into this 24-month open-label extension study (Study MT10109L-004). 	L)
 Participants who complete this study will have an exit visit on Day 720. Number of Participants: 	
All eligible participants who complete the lead-in pivotal Phase 3 studies (MT10109L-001, -0-005, and -006) can enroll in the current study.)02,
Number of Sites:	
All sites from the lead-in Phase 3 studies will participate (approximately 44 global sites).	
Intervention Groups and Study Duration:	
• The total duration of study participation for each participant is approximately 24 months (Day 1/study entry to Day 720/or early exit).	

[figure not shown]
CONFIDENTIAL Protocol MT10109L-004 AMD 5 MT10109L

Data Monitoring Committee: No

Protocol MT10109L-004 AMD 5

1.2. Schema

[figure not shown]
Protocol MT10109L-004 AMD 5

→ Medytox

CONFIDENTIAL

MT10109L

15

2. Introduction

2.1. Study Rationale

The purpose of this open-label, extension study is to evaluate the long-term safety of repeated MT10109L treatment of GL and/or LCL in participants with moderate to severe GL, LCL, or both (GL and LCL) who completed the lead-in pivotal Phase 3 studies (MT10109L-001, -002, -005, and -006) over an additional 24 months.

The clinical development program for MT10109L in the treatment of GL and LCL includes 4 pivotal Phase 3 double-blind, randomized, parallel-group, placebo-controlled, multicenter clinical studies. Each of these studies will provide the primary safety and efficacy data for MT10109L treatment of GL (Studies MT10109L-001 and -005) and LCL (Studies MT10109L-002 and -006). Participants completing these studies will be eligible to enroll into the current 24-month open-label extension study (Study MT10109L-004) and continue their treatment of GL, LCL, or both GL and LCL.

2.2. Background

Glabellar lines are deep furrows or frown lines in the glabellar area of the face and LCL (or CFL) are horizontal smile lines by the sides of the eyes. Both types of facial lines result from the repetitive functional action of the underlying mimetic facial musculature during animation (Blitzer 1993). When injected at therapeutic doses, MT10109L produces partial chemical denervation of the muscle, resulting in localized reduction in muscle activity. Because GL and LCL result from muscular activity, the muscle relaxation leads to a temporary relief of facial lines. While it was previously thought that these facial lines were structural and permanent, the effects of these injections demonstrate the lines are part functional and remain because of constant muscle tone (Ferreira 2004; Garcia 1996).

[figure not shown]
The development of facial lines (such as GL and LCL) is an age-related change of the face that occurs because of the repetitive muscle contractions that are associated with common facial expressions. Thus, these facial lines can be observed with contraction (dynamic rhytides) or in more severe cases in repose (static rhytides). Increasing severity in the appearance of facial lines has been associated with a patient's perception of reduced attractiveness and a negative effect on self-esteem and sense of well-being (Koblenzer 1996). Furthermore, the appearance of these

[figure not shown]
Protocol MT10109L-004 AMD 5

facial lines can lead to a miscommunication of an emotional state of anger, anxiety, disapproval, or sadness (Khan 2001) causing distress and affecting social interactions (Finn 2003).

The popularity of BoNT/A cosmetic treatment of LCL and GL in adults is related to its proven efficacy for reducing moderate to severe facial lines (Beer 2006); well documented safety profile (Brin 2009); and positive impact on psychological well-being and the resulting psychosocial benefits (Finn 2003).

The purpose of this open-label, extension study is to evaluate the long-term safety of repeated MT10109L treatment of GL and/or LCL in participants with moderate to severe GL, LCL, or both (GL and LCL) who completed the lead-in pivotal Phase 3 studies (MT10109L-001, -002, -005, and -006) over an additional 24 months. This information will supplement the primary safety and efficacy data from the 4 pivotal lead-in Phase 3 studies. Together with their lead-in Phase 3 study participation, participants who complete this study will provide up to 3 years of continuous treatment exposure data.

Protocol MT10109L-004 AMD 5

2.3. Benefit/Risk Assessment

Generally, the popularity of BoNT/A cosmetic treatment of GL and LCL in adults is related to its proven efficacy for reducing moderate to severe facial lines (Beer 2006); well documented safety profile (Brin 2009); and positive impact on psychological well-being and the resulting
psychosocial benefits (Finn 2003).

In some cases, botulinum toxin effect may be observed beyond the site of local injection. The symptoms may include asthenia, generalized muscle weakness, diplopia, eyelid ptosis, dysphagia, dysphonia, dysarthria, urinary incontinence, and breathing difficulties. Swallowing and breathing difficulties can be life threatening and there have been reports of death related to distant spread of toxin effects with other BoNT/A treatments for noncosmetic indications. The risk of symptoms is probably greatest in children treated for spasticity, but symptoms can also occur in adults treated for spasticity and other conditions.

Reduced blinking after BoNT/A product injection to the orbicularis muscle can lead to corneal exposure, persistent epithelial defect, and corneal ulceration with perforation. In the use of another BoNT/A product for treatment of blepharospasm, 1 case of corneal perforation in an aphakic eye requiring corneal grafting has occurred because of this effect.

[figure not shown]

CONFIDENTIAL
MT10109L

Protocol MT10109L-004 AMD 5

3. Objectives and Endpoints

^a There are no objectives associated with the efficacy endpoints in this study.

b Baseline is from the lead-in studies for all efficacy endpoints in this study.

Protocol MT10109L-004 AMD 5

4. Study Design

Overall Design 4.1. • All participants who complete studies MT10109L-001 (GL), MT10109L-002 (LCL), MT10109L-005 (GL with or without LCL), and MT10109L-006 (LCL with or without GL) will be eligible to enroll into this 24-month open-label extension study (Study MT10109L-004). Approximately 800 participants will be enrolled at approximately 44 global sites

• Participants who complete this study will have an exit visit on Day 720.

[figure not shown]

Protocol MT10109L-004 AMD 5

4.2. Scientific Rationale for Study Design

4.4. End of Study Definition

The end of the study is defined as the date of the last scheduled procedure shown in the SoA for the last participant in the study globally.

A participant is considered to have completed the study if he/she has completed all phases of the study including the last scheduled procedure shown in the SoA.

Protocol MT10109L-004 AMD 5

[figure not shown]
5. Study Population

Participants who complete Studies MT10109L-001 (GL), MT10109L-002 (LCL), MT10109L-005 (GL with or without LCL), and MT10109L-006 (LCL with or without GL) will be eligible to enroll into this 24-month open-label extension study.

Prospective approval of protocol deviations to recruitment and enrollment criteria, also known as protocol waivers or exemptions, is not permitted.

Protocol MT10109L-004 AMD 5

5.3. Lifestyle Considerations

Screen Failures

No restrictions are required.

5.4.

[figure not shown]

Protocol MT10109L-004 AMD 5

6. Study Intervention

[figure not shown]
Study intervention is defined as any investigational intervention(s), marketed product(s), or placebo intended to be administered to a study participant according to the study protocol.

Retreatment criteria are described in Section 6.6.

Protocol MT10109L-004 AMD 5

6.1.2. Instructions for Use and Administration

Only trained and medically qualified physicians experienced with BoNT/A injections are
authorized to administer the study interventions.

[figure not shown]

CONFIDENTIAL MT10109L	Protocol MT10109L-004 AMD 5
study interventions will be administered as bila sites in the lateral aspect of each orbicularis oc	ed as IM injections at 5 injection sites in the and 1 in the procerus (Figure 6-1 A). The LCL aterally symmetrical IM injections at 3 injection uli (Figure 6-2 A). When GL and LCL are treated or each area will be followed, as described below.
Participants must be observed for adverse ever injection.	its for ≥ 30 minutes after each study intervention
Glabellar Line Injection Technique	

Protocol MT10109L-004 AMD 5

GL and LCL Participants

GL and LCL will be treated together, following the appropriate injection technique for each area, as described above.

6.2. Preparation/Handling/Storage/Accountability

- 1. The investigator or designee must confirm appropriate temperature conditions have been maintained during transit for all study intervention received and any discrepancies are reported and resolved before use of the study intervention.
- 2. Only participants enrolled in the study may receive study intervention, and only authorized site personnel may administer study intervention. All study intervention must be stored in a secure, environmentally controlled, and monitored (manual or automated) area in accordance with the labeled storage conditions with access limited to the investigator and authorized site personnel.
- 3. The investigator, institution, or the head of the medical institution (where applicable) is responsible for study intervention accountability, reconciliation, and record maintenance (ie, receipt, reconciliation, and final disposition records).
- 4. Further guidance and information for the final disposition of unused study interventions are provided in the study manual.

All unused study intervention and empty vials must be returned to the sponsor at the termination of the study. Unit counts will be performed when the study intervention is returned, and all study intervention must be accounted for. Unused drug supplies and empty vials will be returned to the sponsor.

6.3. Measures to Minimize Bias: Randomization and Blinding

This is an open-label study.

The participant's identification number from the lead-in Phase 3 study will be used in this extension study. This will serve as the participant identification number on all study documents.

Protocol MT10109L-004 AMD 5

6.4. Study Intervention Compliance

Participants will receive all doses under the direct supervision of study site personnel. Study intervention compliance will not be calculated.

The study site will keep an accurate drug disposition record that specifies the amount of study intervention administered to each participant and the date of administration.

6.5. Concomitant Therapy

The use of any concomitant medication or vaccine (including prescription or over-the-counter medication, vitamins, and/or herbal supplements) is to be recorded on the participant's eCRF at each visit along with the reason the medication is taken.

At each study visit, study site personnel will question each participant specifically on the use of concomitant medications. Study site personnel must notify the sponsor immediately if a participant consumes any concomitant medications not permitted by the protocol. Participants who admit to using prohibited concomitant medications may be discontinued from the study at the discretion of the investigator or sponsor.

 	 •		

Protocol MT10109L-004 AMD 5

Any medication or vaccine (including prescription or over-the-counter medication, vitamins, and/or herbal supplements) that the participant is receiving at the time of enrollment or receives during the study must be recorded along with:

- Indication
- Dates of administration including start and end dates
- Dosage information including dose and frequency

Therapy considered necessary for the participant's welfare may be given at the discretion of the investigator. If the permissibility of a specific medication/intervention is in question, please contact the sponsor.

The sponsor must be contacted if there are any questions regarding concomitant or prior therapy.

Any medication taken during the study between the date of the first dose of study intervention and the date of the end-of-study visit will be recorded in the eCRF as a concomitant medication; any medication started after the end-of-study visit will not be considered a concomitant medication and should not be captured in the eCRF.

6.5.3. Rescue Medicine

[figure not shown]
Rescue medicine is not applicable.

6.6. Dose Modification

This protocol does not allow for alteration from the currently outlined dosing schedule.

[figure not shown]
Participants entering from the lead-in Phase 3 studies will receive open-label study intervention based on meeting retreatment criteria.

6.7. Intervention After the End of the Study

There is no further intervention following the end of the study.

7. Discontinuation of Study Intervention and Participant Discontinuation/Withdrawal

A premature discontinuation will occur if a participant who signs the ICF ceases participation in the study, regardless of circumstances, before the completion of the protocol-defined study procedures.

Notification of early participant discontinuation from the study and the reason for discontinuation will be made to the sponsor and will be clearly documented on the appropriate eCRF.

Definitions of the standard terms are provided in Appendix 5.

Reasons for discontinuation from the study intervention and/or the study may include the following commonly used terms:

Commonly Used Terms
Adverse event
Lost to follow-up
Lack of efficacy
Other
Physician decision
Pregnancy
Protocol deviation
Site terminated by sponsor
Study terminated by sponsor
Withdrawal by subject

7.1. Discontinuation of Study Intervention

Study intervention must be discontinued for the following reasons:

- Pregnancy (see Appendix 7 and Section 8.3.5. Pregnancy)
- Other safety criteria (eg, hypersensitivity to the study intervention, failure to continue to meet study entry criteria)

Women who test positive for urine pregnancy test will NOT receive further interventions and will be discontinued from the study. They must complete study exit procedures and be followed up for pregnancy outcome. See the SoA for data to be collected at the time of intervention discontinuation and follow-up and for any further evaluations that need to be completed.

Protocol MT10109L-004 AMD 5

7.2. Participant Discontinuation/Withdrawal From the Study

- A participant may withdraw from the study at any time at his/her own requestor may be withdrawn at any time at the discretion of the investigator for safety, behavioral, compliance, or administrative reasons.
- If the participant withdraws consent for disclosure of future information, the sponsor may retain and continue to use any data collected before such a withdrawal of consent.
- See the SoA for data to be collected at the time of study discontinuation and follow-up and for any further evaluations that need to be completed.

7.3. Lost to Follow-up

A participant will be considered lost to follow-up if he or she repeatedly fails to return for scheduled visits and is unable to be contacted by the study site.

The following actions must be taken if a participant fails to return to the study site for a required study visit:

- The study site must attempt to contact the participant and reschedule the missed visit as soon as possible and counsel the participant on the importance of maintaining the assigned visit schedule and ascertain whether or not the participant wishes to and/or should continue in the study.
- Before a participant is deemed lost to follow-up, the investigator or designee must make every effort to regain contact with the participant (where possible, 3 telephone calls and, if necessary, a certified letter to the participant's last known mailing address or local equivalent methods). These contact attempts will be documented in the participant's medical record.
- Should the participant continue to be unreachable, he/she will be considered to have withdrawn from the study.

Discontinuation of specific sites or of the study as a whole are handled as part of Appendix 1.

[figure not shown]

Protocol MT10109L-004 AMD 5

8. Study Assessments and Procedures

[figure not shown]
- Study procedures and their timing are summarized in the SoA. Protocol waivers or exemptions are not allowed.
- Immediate safety concerns must be discussed with the sponsor immediately upon occurrence
 or awareness to determine if the participant should continue or discontinue study
 intervention.
- Adherence to the study design requirements, including those specified in the SoA, is essential and required for study conduct.

	1
•	
•	All assessments must be completed after the participant removes their make-up (if wearing any) and before administration of study intervention.
	 

Protocol MT10109L-004 AMD 5

8.2. Safety Assessments

Planned timepoints for all safety assessments are provided in the SoA.

8.2.1. Adverse Events

The investigator will question the participant to ascertain whether any adverse events were experienced since the previous visit. Additionally, at treatment visits, the participants will be observed for ≥ 30 minutes following study intervention. All pertinent information regarding adverse events (ie, date of onset and stop, duration, outcome, severity, relationship to study intervention, action or treatment required) will be obtained and recorded in the source documents and appropriate eCRF page.

8.2.2. Vital Signs

- Pulse rate (beats per minute): Participants are to be seated for at least 2 minutes, and pulse rate will be counted over 60 seconds and recorded in the source document and eCRF as beats per minute.
- Blood pressure (mm Hg): Participants are to be seated for at least 2 minutes, and systolic/diastolic blood pressure will be measured.
- Respiration rate (breaths per minute): Participants are to be seated for at least 2 minutes, and breaths will be counted for 30 seconds and multiplied by 2.

Protocol MT10109L-004 AMD 5

8.2.3. Urine Pregnancy Test

Urine dipstick kits will be used to conduct pregnancy tests at the timepoints specified in the SoA, or more frequently at the investigator's discretion.

8.2.4. Suicidal Risk Monitoring

Suicidal risk monitoring is not applicable for this study.

8.3. Adverse Events and Serious Adverse Events

The definitions of an adverse event or SAE can be found in Appendix 3.

Adverse events will be reported by the participant.

The investigator and any qualified designees are responsible for detecting, documenting, and recording events that meet the definition of an adverse event or SAE and remain responsible for following up adverse events that are serious, considered related to the study intervention or study procedures, or that caused the participant to discontinue the study intervention (see Section 7).

The following expected adverse drug reactions are based on BOTOX clinical trial data for the treatment of GL and LCL (Tables 8-1 and 8-2, respectively).

Table 8-1 Expected Adverse Reactions for Treatment of Glabellar Lines

Expected Adverse Reactions ^a	Incidence
Eyelid ptosis	3%
Facial pain	1%
Facial paresis	1%
Muscular weakness	1%

^a Data are based on BOTOX glabellar lines clinical trial data (BOTOX Cosmetic US Package Insert, 2017)

Table 8-2 Expected Adverse Reactions for Treatment of Lateral Canthal Lines

Expected Adverse Reactions ^a	Incidence
Eyelid oedema	1%

^a Data are based on BOTOX lateral canthal lines clinical trial data (BOTOX Cosmetic US Package Insert, 2017)

The adverse drug reactions of eyelid edema, eyelid ptosis, facial pain, facial paresis, and muscular weakness with BOTOX are usually mild in severity, reversible, and have a low

Protocol MT10109L-004 AMD 5

incidence. Therefore, no treatment for these reactions is recommended. If these reactions are moderate or severe, medical help should be sought as needed.

8.3.1. Time Period and Frequency for Collecting Adverse Event and Serious Adverse Event Information

All adverse events will be collected from the signing of the ICF at the timepoints specified in the SoA (Section 1.3), and as observed or reported spontaneously by study participants until 30 days after the participant's last study visit.

Medical occurrences that begin before the start of study intervention, but after obtaining informed consent will be recorded in the adverse event section of the eCRF.

All SAEs will be collected from the signing of the ICF study at the timepoints specified in the SoA (Section 1.3), and as observed or reported spontaneously by study participants, until at least 12 weeks after the participant's last administration of MT10109L intervention.

All SAEs will be recorded and reported to the sponsor or designee within 24 hours, as indicated in Appendix 3. The investigator will submit any updated SAE data to the sponsor within 24 hours of it being available.

Investigators are not obligated to actively seek adverse event or SAE information after conclusion of the study participation. However, if the investigator learns of any SAE, including a death, at any time after a participant has been discharged from the study, and he/she considers the event to be reasonably related to the study intervention or study participation, the investigator must promptly notify the sponsor.

The method of recording, evaluating, and assessing causality of adverse events and SAEs and the procedures for completing and transmitting SAE reports are provided in Appendix 3.

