9.4.2.1. Adverse Events

_	

An adverse event that occurs more than 30 days after study exit will not be counted as a TEAE.

An adverse event will be considered a TESAE if it is a TEAE that additionally meets any SAE criteria.

The number and percentage of participants reporting TEAEs in each study intervention group will be tabulated by system organ class and preferred term and by system organ class, preferred term, and severity

The number and percentage of participants reporting treatment-related TEAEs in each study intervention group will be tabulated by system organ class and preferred term by MT10109L cycle.

If more than 1 adverse event is coded to the same preferred term for the same participant, the participant will be counted only once for that preferred term using the most severe and most related occurrence for the summarizations by severity and by relationship to MT10109L intervention.

Protocol MT10109L-004 AMD 5

Summary tables will be provided for participants with SAEs and participants with adverse events leading to discontinuation if 5 or more participants reported such events. Listings of all adverse events, SAEs, and adverse events leading to discontinuation by participant will be presented.

The definitions of an adverse event and SAE can be found in Appendix 3.

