## 1.2. Study Design

#### **Overall Study Design:**

- Global, multicenter, open-label, repeat treatment, parallel-group
- Treatment Group: MT10109L administered in the same treatment area(s) with the same number of injections and injection sites as in their lead-in Phase 3 study.
- Study Duration: 24-month treatment period
- Participants ≥ 19 years old who completed Studies MT10109L-001 (GL), MT10109L-002 (LCL), MT10109L-005 (GL with or without LCL), and MT10109L-006 (LCL with or without GL) and meet study entry criteria may receive up to 9 study interventions in Study MT10109L-004
- Approximately 800 participants will be enrolled at approximately 44 global sites
- Based on meeting retreatment criteria for each intervention, the first intervention in this study may occur at the Day 1 visit and the last intervention may occur at the Day 690 visit (30 days prior to Day 720/study exit).
- \_\_\_\_\_\_
- Participants who complete this study will have an exit visit on Day 720.

[figure not shown]

[figure not shown]

[figure not shown]
Statistical Analysis Plan

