## 5.1.1. Treatment Group and Treatment Cycles

All safety and efficacy analyses will be integrated analyses that include data from both the leadin studies and the MT10109L-004 extension study, for participants enrolled into the extension study.

A study treatment cycle is considered to start on the day of treatment with study intervention and end on the day prior to the next study intervention or on the study exit day if there are no subsequent interventions. The nomenclature used will be "treatment cycle 1", "treatment cycle 2", "treatment cycle 3", "treatment cycle 4", "treatment cycle 5", "treatment cycle 6", "treatment

cycle 7", "treatment cycle 8", "treatment cycle 9", "treatment cycle 10", "treatment cycle 11", and "treatment cycle 12" for the lead-in and extension study possible treatment regimen cycles.

Demographic and baseline characteristic, disposition, treatment-emergent adverse event (TEAE) for entire study, vital signs, and immunogenicity tables will be summarized under leadin and extension study possible treatment regimens specified in Table 5-3. It will use planned treatment in lead-in study/ planned treatment in extension study for lead-in and extension study possible treatment regimens.

In general, there will be no substitution of missing time or date. However, any partial information will be utilized to its full extent wherever sensible. For example, a medication may be classified as a prestudy medication if the partial information of the medication ending date with only month and year permits a determination that the medication ended prior to the injection date of the study intervention.

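### The 12-week SAE collection window does not match the post-exit reporting rule, the TESAE cut-off or the end of the last treatment cycle

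*Protocol*

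**What the plan says.** - **Collection windows (Protocol 8.3.1).** AEs are collected at scheduled timepoints "and as observed or reported spontaneously by study participants until 30 days after the participant's last study visit". SAEs of any cause are collected in the same way, but until at least 12 weeks after the "last administration of MT10109L intervention".
- **After participation (Protocol 8.3.1, later paragraph).** "Investigators are not obligated to actively seek adverse event or SAE information after conclusion of the study participation". If the investigator nevertheless hears of an SAE after discharge, the sponsor must be told if the investigator considers it related to the treatment or to taking part.
- **End of participation (Protocol 1.1).** "The total duration of study participation for each participant is approximately 24 months (Day 1/study entry to Day 720/or early exit").
- **Latest injection (SAP 1.2).** "the last intervention may occur at the Day 690 visit (30 days prior to Day 720/study exit").
- **TEAE cut-off (Protocol 9.4.2.1).** "An adverse event that occurs more than 30 days after study exit will not be counted as a TEAE". SAP 5.3.1.1 uses the same 30-day limit. Both documents define a TESAE as a TEAE that also meets a seriousness criterion.
- **Treatment cycles (SAP 5.1.1).** A cycle ends the day before the next injection, "or on the study exit day if there are no subsequent interventions". SAP 5.3.2.1 reports AE incidence by MT10109L cycle as well as over the whole study.

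**The concern.** Three rules that should share one end date have different ones: SAE collection is tied to the last injection, TESAE counting to study exit plus 30 days, and the last cycle to study exit itself.

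The first consequence is for sites. An unrelated SAE that begins after exit but within 12 weeks of the last injection is reportable under the collection sentence. Under the post-discharge sentence there is no stated duty to report it. Two sites could handle the same event differently, and both could point to 8.3.1.

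The second is for the tables. An SAE that the protocol requires to be collected can fall after the TEAE cut-off and so cannot enter the TESAE rows. A TEAE in the 30 days after exit counts in the whole-study table, but the visible SAP gives it no cycle. Incidence of adverse events is a primary endpoint, and long-term safety is the objective of the study, so the counting rules should be unambiguous.

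**Working it through.** **Inputs**
- Exit for completers: Day 720 (Protocol 1.1 and 4.1).
- Latest injection: Day 690 (SAP 1.2).
- SAE window: at least 12 weeks = 84 days from the last injection (Protocol 8.3.1).
- TEAE and TESAE cut-off: exit + 30 days (Protocol 9.4.2.1, SAP 5.3.1.1), so 720 + 30 = Day 750 for completers.

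**The plan's own figure.** The SAP gives 30 days between the last possible injection and exit: 720 - 690 = 30. This reproduces.

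**Formulas**, for a completer last injected on day *d*:
- Window end = *d* + 84.
- Window days after exit = max(0, *d* + 84 - 720).
- Window days outside the TESAE count = max(0, *d* + 84 - 750).

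| Last injection | Window ends | Days after exit | Days outside TESAE count |
|---|---|---|---|
| Day 636 | Day 720 | 0 | 0 |
| Day 666 | Day 750 | 30 (36%) | 0 |
| Day 678 | Day 762 | 42 (50%) | 12 (14%) |
| Day 690 | Day 774 | 54 (64%) | 24 (29%) |

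Percentages are of 84 days. At Day 690 the uncounted stretch is Days 751 to 774.

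**Thresholds for completers.** The window outlasts exit only if *d* > 720 - 84 = 636. TESAE days are lost only if *d* > 750 - 84 = 666. More than half the window lies after exit only for last injections from Day 679 to Day 690.

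**Sensitivity to day counting.** If the injection day counts as day 1, the Day 690 window ends at Day 773, with 53 days after exit and 23 outside the TESAE count. The conclusion is unchanged.

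**Early exits.** For exit *g* days after the last injection, 84 - *g* window days follow exit when *g* < 84, and 54 - *g* fall outside the TESAE count when *g* < 54. As an illustration (*g* = 10 is assumed), these are 74 and 44 days.

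**Cycle check.** The last cycle ends at Day 720 for a completer, while TEAEs are accepted to Day 750. All 30 of those days lie outside every cycle as defined, whenever the last injection was given.

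**The case against.** Several stronger readings are tempting, and the documents do not support them.

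*That the protocol promises active follow-up and then withdraws it.* After the last visit, 8.3.1 offers only scheduled timepoints and events that are observed or spontaneously reported. A window of spontaneous reports is compatible with having no duty to ask. The schedule of activities is not visible and could include a post-exit contact: SAP 1.2 mentions telephone visits, and Protocol 8.3.3 mentions a follow-up period distinct from participation. What remains is the difference in scope, all SAEs in one sentence and only related ones in the other.

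*That late SAEs are never counted.* They are outside the TESAE rows, but Protocol 9.4.2.1 lists all SAEs and tabulates participants with SAEs if at least 5 report them. SAP 5.3.2.1 summarises SAEs regardless of cause, and the SAP's SAE definition has no time limit. A reported late SAE will reach the listings and possibly those summaries.

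*That the final injection is always less well observed than earlier ones.* A completer last injected by Day 636 has the full 84 days within participation.

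*That post-exit TEAEs certainly drop out of the cycle tables.* The AE listing carries a cycle for each event, and SAP 6.4.5 refers to an onset cycle, so some assignment is intended. No visible text says how it treats events after exit, and parts of SAP 5.1 are not shown. The gap in the definition stands.

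*That the safety rates are materially biased down.* At worst, 24 days are uncounted against 750 counted days in the extension (24/750 = 3.2%), before lead-in time is added. The size of any bias cannot be established.

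**Conclusion.** The point holds as a mismatch between rules. Protocol 8.3.1 conflicts with itself on unrelated SAEs after exit. The TESAE cut-off ends up to 24 days before the minimum SAE window for completers, and earlier still relative to that window for some early exits. Post-exit TEAEs have no cycle under SAP 5.1.1.

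The conclusion rests on three assumptions: participation ends at exit, as the synopsis states; Day 690 is the latest injection, which appears only in the SAP in the visible text; and 12 weeks is taken as 84 days. The share of participants last injected after Day 636 or Day 666, or exiting soon after an injection, is not given. The number of events affected is therefore unknown and may be small. A reader might infer that late SAEs vanish or that reported rates are seriously understated; neither follows. The changes are still worth making, because they settle the counting rules behind a primary safety endpoint at almost no cost.

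**What to change.** 1. **Protocol 8.3.1.** Reconcile the two paragraphs so that all SAEs, whatever their cause, are reportable to the end of the 12-week window. Limit the related-only rule to the time after that. If the schedule of activities has no post-exit contact, state how SAEs are ascertained between exit and the end of the window. A telephone call is one option, but it is a design preference and not something the documents already require.
2. **Protocol 9.4.2.1 and SAP 5.3.1.1.** Count as TESAEs all SAEs with onset up to the later of 30 days after exit and 12 weeks after the last injection. Carry the same exception for serious events into the TEAE definition, so that TESAEs remain a subset of TEAEs.
3. **SAP 5.1.1.** State that, for AE tables, TEAEs with onset after exit belong to the last treatment cycle, including any late SAEs admitted by the second change.

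The cost is wording in both documents and a possibly slightly higher reported TESAE rate. Serious and non-serious events would then have different end dates in some participants, which a table footnote should state.
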